5.3 Protection of Vulnerable Subjects

The study activities cannot otherwise be performed without the use of vulnerable populations. Vulnerable subjects are individuals whose willingness to volunteer in a clinical investigation could be unduly influenced by the expectation, whether justified or not, of benefits associated with participation or of retaliatory response from senior members of a hierarchy in case of refusal to participate.

The Sponsor shall avoid improper influence on, or inducement of, the subject, monitor, any investigator(s), or other parties participating in, or contributing to, the clinical investigation.

All investigators shall avoid improper influence on, or inducement of, the subject, Sponsor, monitor, other investigator(s), or other parties participating in, or contributing to, the clinical investigation.

5.3.1 GE Employees

Direct employees of GE may participate as subjects in this study. These subjects will be protected from coercion or undue influence at all times, and participation in this study and study results will not be considered in any decisions related to education or employment. Information about research participation and outcomes will not be made available to the employee's manager/supervisor. Information about employees collected during the study will not be revealed to others within the company except as necessary to conduct the study. Employees may be asked for personal and corporate identification information as necessary to conduct and reimburse participants, in accordance with local laws and regulations. Identifiable information will be removed from any study data used or stored outside of the study for engineering development or other purposes as such that it cannot be reasonably linked the employee participant in the future.

5.3.2 Safeguards for GE Employees

General Electric (GE) Ultrasound employees and Ultrasound contractors are not eligible to participate in this study. Recruitment materials will state that there is no requirement for GE employees to participate in this research Study and there will be no consequences for anyone who does not volunteer.

5.3.3 Additional Study-Specific Risk Mitigations

Ultrasound scans conducted in this study will not require any medical or biologic administrations including intravenous contrast agent. Further, no study scans will require any invasive techniques and only transcutaneous scanning will be performed.

Study Title: Development Of Medical Ultrasound Systems, Accessories, And

Components - GE Bangalore

Study Number: 110.08-2015-GES-0004

5.4 Inclusion Criteria

Subjects must meet all of the following:

1. Aged 18 years or older;
2. Able and willing to provide written informed consent in accordance with the PNDT Act in India;
3. Able to understand and respond in English;
4. General Electric (GE) employee or contractor at the John F. Welch Technology Centre (JFWTC) facility.

5.5 Exclusion Criteria

Subjects must not meet any of the following:

1. Direct employee or contractor of the General Electric (GE) Ultrasound business at the John F. Welch Technology Centre (JFWTC) facility;
2. If female, pregnant or unsure of her pregnancy status per self-report.
3. Is not able to or would be put at additional risk from completing study activities, in the opinion of the study staff;
4. Subjects who have an electronic medical device at the time of the study scan (such as pacemaker, implantable cardioverter/defibrillator, insulin pump, cochlear implant, or other implanted electronic medical device).

5.6 Recruitment and Scheduling

Potential subjects will be recruited from the GE facility using IRB/EC-approved methods detailed in the study Recruitment Plan, which may include electronic materials, paper materials, and/or word-of-mouth. To evaluate devices across different population sub-groups, some recruitment efforts may be focused on reaching specific population sub-groups, including but not limited to: gender, age, or body type. As allowable per IRB/EC policy, this study may also recruit from eligible subjects already participating in other research activities Sponsored by GEHC that have consented to be contacted by GEHC for future studies. Enrolled subjects who agree to be re-contacted will constitute a pool of individuals upon which to draw for future study scans. Subjects may be scheduled for additional visits in a non-randomized order to ensure an appropriately representative subset of subject characteristics is tested for each device under study.

5.7 Screening Subjects for Enrollment

Subjects may be pre-screened via telephone or email following IRB/EC-approved scripts to assess potential eligibility.

Informed consent will be obtained as described in the Informed Consent and Privacy Requirements section. Upon agreeing to participate in the Study, the subject will sign and date the ICF. The subject will be assigned an identification code unique to the subject (i.e. next sequential number on the enrollment log). A subject's enrollment in the study begins when he/she completes the above Informed Consent process and is assigned a unique study identification code.

Study Title: Development Of Medical Ultrasound Systems, Accessories, And

Components - GE Bangalore

Study Number: 110.08-2015-GES-0004

After the subject has completed the informed consent process, Study Staff will verify that he or she meets all of the inclusion criteria and none of the exclusion criteria. Determination of eligibility relies on information reported by the subject. The Study Staff may or may not have necessary medical training or licensure to confirm subject self-reported health status and will not make independent assessments.

Subjects may participate more than once throughout the study's duration. Eligibility will be documented at the subject's first visit, and for any subsequent visits it will be confirmed that the subject remains eligible per the inclusion/exclusion criteria prior to the study scan.

5.8 Enrollment

Following recruitment, a subject will be considered enrolled (the point of enrollment) once he/she signs and dates the informed consent form (ICF). Once enrolled, the subject will be assigned a unique subject number, which will not contain information that could identify the subject (such as subject name or date of birth). The unique subject number will be used to label case report form (CRF) data for the subject throughout his/her participation in the study.

5.9 Screen Failures

Subjects that do not meet all inclusion and exclusion criteria will be considered screen failures. Subjects who leave the study should be counted as withdrawals per [Section 6.8. Discontinuation and Withdrawal Criteria](#) rather than screen failures.

5.10 Discontinuation/Withdrawal Criteria

5.10.1 Discontinuation of a Scan

Subjects may decide to discontinue (not participate or end participation) during any study scan without any negative repercussions. A subject may choose to discontinue or be discontinued by Study Staff from a study scan. If this occurs, all data and images collected prior to discontinuation will be used. If a subject discontinues a study scan, he or she will still be considered enrolled in the study and eligible for future study scans unless specifically documented as withdrawn from the study.

5.10.2 Study Withdrawal

The subject may withdraw from study participation at any time, for any reason without consequence. The Study Staff may withdraw a subject at any time for any reason. The reason for withdrawal for any subject will be recorded and reported to the Sponsor. The IRB/EC is to be notified per their notification of subject withdrawal policy. Withdrawn subjects may not participate in future study scans unless they are re-enrolled. Subjects should only be considered withdrawn if they do not wish to participate or are ineligible for all future study scans.

6. STUDY PROCEDURES

6.1 Protections and Safeguards

Participation in Multiple Study Visits – Enrolled subjects may be eligible for one or more research study visit. The Investigator or study staff may limit the number or duration of visits for any subject if it is suspected that the subject is under undue influence to participate, if participating could pose a risk to the subject's physical or mental

Study Title: Development Of Medical Ultrasound Systems, Accessories, And

Components - GE Bangalore

Study Number: 110.08-2015-GES-0004

health, or for any other reason, in the opinion of the study staff. Subjects that have already been screened for enrollment, provided consent, and undergone necessary safety and eligibility screening to participate may participate in additional study visits if the subject:

- has provided written informed consent using the current IRB/EC-approved consent version (subjects should be re-consented if previously consented using an older version of the consent form).
- remains eligible according to the inclusion/exclusion criteria on the day of the procedure.

6.1.1 Handling of Requests for Physician Notification

Upon subject request, a notification form describing the subject's enrollment in this study will be sent to the subject's primary physician.

6.1.2 Activities prior to a Study Scan

For some ultrasound devices, there may be a risk of interference with electronic medical devices. Subjects will be asked if they have an electronic medical device (for example pacemakers, insulin pumps, defibrillators, hearing aids, among others). Subjects who report having a removable hearing aid may be asked to remove the hearing aid during the study scan.

Prior to scanning, subjects may be asked to move, remove, or change their clothing, or to change into a gown, in order to allow access to the target anatomical region(s) for scanning. A private area (enclosed room or curtained area) will be provided for subjects that are required to change clothes.

As necessary for the scanning procedures, subjects may be asked to perform conventional pre-scanning maneuvers or activities similar to those required for clinical ultrasound procedures, such as positioning themselves in certain ways or withholding urination in order to have a partially full bladder during scanning. None of these activities should cause discomfort. For subjects asked to have a partially full bladder, a break to empty the bladder will be provided at any time upon request, and subjects may still participate if they decline to have a partially full bladder. The skin surface may be cleaned before scanning.

6.1.3 Activities during a Study Scan

Each subject may elect to participate in up to five (5) study scans per day lasting up to 60 cumulative minutes each with approximately a 15 minute break before starting another study scan. Ophthalmic scanning will be limited to no more than 15 cumulative minutes of scan time per eye, per day.

The start time of a study scan begins when the device contacts the subject's skin and scanning begins; the stop time is when the study scan is complete. Pauses in active scanning are not counted towards the cumulative scan duration.

The study ultrasound scan will be performed while the subject is lying, sitting, or standing. Subjects may be asked to shift positions, to hold still, complete breath hold(s), bear down (Valsalva maneuver), or other maneuvers necessary for the scanning procedure. In some cases, device accessories (e.g. coupling agents, probe, land marking, tracking, monitoring, or other ultrasound device components) may be placed in direct contact with the subject's skin and/or superficial marks may be placed with a semi-permanent medical grade marker.

Scanning may be performed for target anatomic areas using a variety of non-invasive, transcutaneous techniques, such as scanning abdominal, musculoskeletal, breast(s), peripleural, transcranial, ophthalmic, cervical/neck, cardiac, vascular, extremity, soft tissue, and other accessible anatomical regions. More than one region may be scanned in a single study scan.

Study Title: Development Of Medical Ultrasound Systems, Accessories, And Components - GE Bangalore

Study Number: 110.08-2015-GES-0004

If a subject reports discomfort or wishes to stop the scan for any reason, the Study Staff will respond to subject's concerns and adjust the scanning procedures or, if the concern is not able to be resolved, discontinue the study scan. There will be no negative repercussions to the subject for reporting discomfort or deciding to stop the study scan, and he/she may still participate in future visits. Non-medical care will be provided to the subject to alleviate any discomfort, as needed.

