1.3 Device Risk and Benefit Analysis

Diagnostic ultrasound devices, components, and accessories are generally considered non-significant risk devices that safely and effectively use reflection of sound waves from different tissues in the human body to generate images. Ultrasound devices have a consistent safety and bioeffect profile that has been studied and reported.^{16, 17} Diagnostic ultrasound devices have been used since the 1950s and are considered one of the safest imaging modalities available. No confirmed adverse biological effects on humans have been reported, though it is possible that the short-term and long-term biological effects of ultrasound are not completely known.^{13, 18}

The possibility of adverse health effects from the sound waves produced by diagnostic ultrasound systems is remote. Ultrasound imaging devices used in this study typically adhere to the exposure limits set forth in the *WFUMB Recommendations on Non-medical Use of Ultrasound* (2013)¹⁹ and the *British Medical Society Guidelines for the Safe Use of Diagnostic Ultrasound Equipment* (2009), as detailed in the safety appendix.²⁰ These standards are employed extensively in other ultrasound studies conducted by the Sponsor. Factors involved in the dose of energy delivered to tissue include the ultrasonic power level and volume of tissue exposed. Prudent and widely accepted limitations are employed in this study to the exposure time and power level during use (as detailed in [Appendix B: SAFETY GUIDELINE TRAINING MATERIALS](#)).

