1.4 Justification

Ultrasound device development is an iterative process that involves engineers making changes and adjustments and then evaluating those updates using human subjects. The process listed above is repeated until the product is functioning optimally. One of the key aspects of this process involves the engineer and the Device Operator viewing images together and discussing the performance of the features and changes under development during the study scan. In order for this cycle to function both efficiently and economically, it is critical that the human scanning occur in the same location as the Research and Development teams (i.e., onsite at Bangalore facility).

The expertise for the product development of the ultrasound devices in use under this study resides at the GEHC Bangalore site. In particular, not only the personnel expertise, but certain specialized testing hardware and software to enable development of these ultrasound devices, components and accessories are located at the Bangalore site.

- Facility expertise for product development includes:
- Feasibility; new features and console-transducer pairings need to be evaluated.
- Verification and Validation; necessary components of the design control cycle.
- Image Quality; the primary determinant of the commercial success of an ultrasound device; and determined by a complex matrix of inputs.
- Complaint Resolution; replication of device complaints in a laboratory controlled setting is an essential part of post-market surveillance.
- Usability testing; to fulfill the requirement for products to have usability testing prior to completion of design input requirements.
- System performance with new hardware and software features.

Study Title: Development Of Medical Ultrasound Systems, Accessories, And

Components - GE Bangalore

Study Number: 110.08-2015-GES-0004

- Ergonomics and Human Factors; essential part of safe, efficient, and successful product design.

In summary, this study needs to be performed at the Bangalore site because the location contains:

1. Controlled Laboratory setting;
2. Engineering expertise;
3. Clinical domain expertise;
4. User preferences (image quality, presets, knobology) expertise;
5. Competitive benchmarks; and
6. Clinical marketing teams.

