APPENDIX B: SAFETY GUIDELINE TRAINING MATERIALS

Figure B.1 – Non-Obstetrical Scanning²⁰

Application	Values to monitor (A)	Thermal Index value		Mechanical Index value	
		0 – 1.0	> 1.0	0 - 0.3	> 0.7
General abdominal	Usually TIB and MI.	✓	(B) restrict time to 1.0<TIB≤1.5 : 120 min 1.5<TIB≤2.0 : 60 min 2.0<TIB≤2.5 : 15 min 2.5<TIB≤3.0 : 4 min 3.0<TIB≤4.0 : 1 min 4.0<TIB≤5.0 : 15 sec 5.0<TIB≤6.0 : 5 sec TIB>6: not recommended	✓	(C) risk of cavitation with contrast agents
Peripheral vascular	[use TIC and MI if bone closer than 1 cm; TIS and MI only if bone does not come into the image]				
Unlisted applications					
Eye	TIS and MI recommended	✓	Scanning of the eye is not recommended	✓	(C) risk of cavitation with contrast agents
Adult transcranial (imaging and stand-alone) (D)	TIC and MI	✓	(B) restrict time to 0.7<TIC≤1.0 : 60 min 1.0<TIC≤1.5 : 30 min 1.5<TIC≤2.0 : 15 min 2.0<TIC≤2.5 : 4 min 2.5<TIC≤3.0 : 1 min TIC>3: not recommended	✓	(C) risk of cavitation with contrast agents
Peripheral pulse monitoring	TI or MI are not usually available for dedicated peripheral pulse monitors.	The output from CW Doppler devices intended for monitoring peripheral pulses is sufficiently low that their use is not contra-indicated, on safety grounds			

✓: There is no known reason to restrict scanning times in this region.
 A: Many scanners allow MI and one of the TI values to be displayed simultaneously: the most appropriate TI value depends on the clinical application.
 B: TI > 1.0 - the overall exposure time (including pauses) should be restricted.
 C: MI > 0.7 - there is a risk of cavitation if an ultrasound contrast agent containing gas micro-spheres is being used. There is a theoretical risk of cavitation without the presence of ultrasound contrast agents. The risk increases with MI values above this threshold.
 D: Transcranial ultrasound investigations may require higher acoustic output or longer monitoring times than other applications. When times longer than those recommended here are required, it is recommended that monitoring is paused regularly to minimise exposure.

For ophthalmic applications, the maximum attainable value for the Thermal Index should be less than or equal to 1, the maximum attainable value of the Mechanical Index should be less than or equal to 0.23 and the maximum attainable value of the derated spatial peak time average intensity, $I_{spta,3}$ should be less than or equal to 50 mW/cm².

End of Document

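### Section 6.1.3 caps a scan at 60 minutes without counting pauses and without reference to Appendix B, so a scan within 6.1.3 can exceed the Appendix B time for its thermal index

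*Protocol*

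**What the plan says.** Section 6.1.3 sets the operating limit: "Each subject may elect to participate in up to five (5) study scans per day lasting up to 60 cumulative minutes each", with a break of about 15 minutes between scans and a separate ceiling of 15 cumulative minutes per eye per day. It then fixes how time is counted: "Pauses in active scanning are not counted towards the cumulative scan duration". It does not mention TI or Appendix B.

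Appendix B, Figure B.1, gives permitted times by application and TI band, for example "1.5<TIB≤2.0 : 60 min" and "2.0<TIB≤2.5 : 15 min". Note B, attached to these times, says that for TI above 1.0 "the overall exposure time (including pauses) should be restricted".

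Section 1.3 connects the appendix to the study: "Prudent and widely accepted limitations are employed in this study to the exposure time and power level during use", and it points to Appendix B for the detail.

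Section 6.1.4 requires staff to record how long the subject was exposed in each scan. It does not say whether pauses belong in that figure, and its list of recorded items does not include TI.

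**The concern.** Two time limits apply to the same scan, and they differ in two ways. They count time differently, since 6.1.3 stops the clock during a pause and note B keeps it running. They also differ in form: 6.1.3 is one flat number, whereas Appendix B falls steeply as TI rises. The procedure section gives the operator only the flat number and the clock that excludes pauses.

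The band 1.5<TIB≤2.0 is the easiest place to go wrong. Both limits read 60 min there, so a reader would naturally take them to be the same rule.

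Pauses are foreseeable. Section 6.1.3 has a rule for them, section 6.1.2 allows a bladder break on request, and section 1.4 describes "the engineer and the Device Operator viewing images together and discussing the performance of the features and changes under development during the study scan" as a key part of the work.

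What is at stake is when an operator stops or lowers output. The primary endpoint (number and type of scans) and the adverse event listing are not affected.

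**Working it through.** The protocol states no figure that reconciles the two limits, so there is none to reproduce. The check is direct arithmetic for a single scan, assuming TI stays in one band throughout.

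**Inputs.** Active time A = 60 min, the 6.1.3 maximum. L = the Appendix B time for the band (Figure B.1). P = total pause time, which the protocol does not give.

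**Step 1: pause that fits before the Appendix B time is passed.** Under note B, elapsed time = A + P, so the spare pause time is L − A. A negative value means that the limit is passed with no pause.

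| Band | L | L − 60 (min) |
|---|---|---|
| TIB 1.0–1.5 | 120 min | 60 |
| TIB 1.5–2.0 | 60 min | 0 |
| TIB 2.0–2.5 | 15 min | −45 |
| TIB 2.5–3.0 | 4 min | −56 |
| TIB 3.0–4.0 | 1 min | −59 |
| TIB 4.0–5.0 | 15 s | −59.75 |
| TIB 5.0–6.0 | 5 s | −59.92 |
| Transcranial TIC 0.7–1.0 | 60 min | 0 |
| Transcranial TIC 1.0–1.5 | 30 min | −30 |
| Transcranial TIC 1.5–2.0 | 15 min | −45 |
| Transcranial TIC 2.0–2.5 | 4 min | −56 |
| Transcranial TIC 2.5–3.0 | 1 min | −59 |

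There are three cases:
- At TIB 1.0–1.5, pauses must total more than 60 min before anything is exceeded.
- In the two 60-min bands, any pause exceeds the time.
- At TIB above 2.0 or transcranial TIC above 1.0, a full 6.1.3 scan exceeds the time with no pause.

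The wording of note B refers to TI above 1.0, but the transcranial entry that carries the B mark begins at 0.7. I take the mark to cover the whole entry.

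**Step 2: size in the equal-limit bands (L = 60).** The pause lengths are assumed.
- P = 5, 10 or 20 min: elapsed = 60 + P = 65, 70 or 80 min.
- As a share f of elapsed time, elapsed = 60/(1 − f). For f = 0.10, 0.25 or 0.40 this gives 60/0.90 = 66.7, 60/0.75 = 80 or 60/0.60 = 100 min. Relative to 60 min these are 1.11, 1.33 and 1.67.

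**Step 3: an operator who applies an Appendix B time but uses the 6.1.3 clock.** At TIB 2.0–2.5, 15 active minutes at the same shares last 15/0.90 = 16.7, 15/0.75 = 20 or 15/0.60 = 25 min against 15. So the counting rule matters even when the right number is used.

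**Step 4: what elapsed counting would leave.** In a 60-min band, 10 or 20 min of pauses leave 60 − 10 = 50 or 60 − 20 = 40 active minutes. At the three shares, 60 × (1 − f) = 54, 45 or 36.

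**Ophthalmic scanning.** Figure B.1 gives no time for the eye above TI 1.0. It advises against scanning there, so this conflict does not arise.

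**The case against.** The strongest reply is that these are two ceilings on two quantities, and staff can keep both by running two clocks. Meeting one ceiling does not license breaching the other. Section 1.3.1 also commits to monitoring scan time, dwell time and acoustic output. This stands, and it rules out calling the two rules mutually exclusive. It does not remove the gap, because nothing in section 6 tells the operator that a second clock exists.

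Appendix B is also softer than a binding limit. It is guideline training material, note B says that time should be restricted, and section 1.3 says devices typically adhere to the cited guidelines. The firm commitment, in section 1.3.1, is to the FDA limits. This too stands, so the right description is exceeding a guideline time that the protocol says it employs.

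The size rests on assumptions: a full 60 active minutes, TI constant in one band, and invented pause lengths. One scan may cover several regions, and section 1.4 does not say that scanning stops during discussion. All of this is correct. The results with no pause do not depend on pause length, but they still assume a full-length scan in one band.

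Note D says of long transcranial work that "it is recommended that monitoring is paused regularly to minimise exposure", so pauses are protective. That is a reason to regard the excess in the equal-limit bands as minor. It does not change how note B counts time.

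A reader might infer that the protocol directs staff past a safety limit, or that subjects will be overexposed. The documents support neither. They do not say how often scans run at high TI or for the full hour, and they leave both limits in force. A reader might also infer that pause counting is the whole problem. It is not, because in the higher bands the flat 60-minute cap is already longer than the Appendix B time.

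**Conclusion.** The point holds as an unreconciled pair of time limits. Compliance with 6.1.3 does not ensure compliance with the Appendix B times that section 1.3 relies on. In the two bands where both limits are 60 min, the pause rule alone makes the difference. At TIB above 2.0 or transcranial TIC above 1.0, a full-length 6.1.3 scan is over the Appendix B time whatever the pauses. At TIB 1.0–1.5 the conflict has little practical force.

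In the equal-limit bands the effect is small: the excess equals the pause time, and active exposure remains within 60 min. In the higher bands the gap between the two numbers is wider, but the protocol does not show how often such scans would occur. This is a modest safety clarification that is worth making because it costs little. The conclusion rests on reading section 1.3 as bringing the Appendix B times into the study, and on the B mark covering the transcranial band that starts at 0.7.

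**What to change.** Add to 6.1.3: *The exclusion of pauses applies only to the 60-minute and 15-minute per-eye limits of this section. Whenever Appendix B gives a time for the application and displayed TI (including transcranial TIC above 0.7), that time also applies, is counted as elapsed time including pauses, and the shorter limit governs.*

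The trigger should be the existence of an Appendix B time and not TI above 1.0, because the latter would miss the transcranial band 0.7<TIC≤1.0.

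In 6.1.4, state whether the recorded exposure duration is active or elapsed time. If it is active time, that item alone cannot show that an Appendix B time was kept.

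The cost is a short text change, a definition for one recorded item and a mention in protocol training. No numerical limit changes. The downside is that some scans at higher TI must end, or have their output lowered, sooner than 6.1.3 alone would require.
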